5.3. Lifestyle Considerations

Potential participants must be willing and able to adhere to the following lifestyle restrictions during the course of the study to be eligible for participation:

1. Refer to Section 6.5, Concomitant Therapy for details regarding prohibited and restricted therapy during the study.
2. Agree to follow all requirements that must be met during the study as noted in the Inclusion and Exclusion Criteria (eg, contraceptive requirements).

5.4. Screen Failures

Participant Identification, Enrollment, and Screening Logs

The investigator agrees to complete a participant identification and enrollment log to permit easy identification of each participant during and after the study. This document will be reviewed by the sponsor study-site contact for completeness.

The participant identification and enrollment log will be treated as confidential and will be filed by the investigator in the study file. To ensure participant confidentiality, no copy will be made. All reports and communications relating to the study will identify participants by participant identification and age at initial informed consent. In cases where the participant does not initiate the study intervention, the date seen and age at initial informed consent will be used.

6. STUDY INTERVENTION

6.1. Study Interventions Administered

Apalutamide will be administered on a continual basis with the following dosage rule, but for the purpose of scheduling the study assessments and treatment compliance, a treatment cycle is defined as 28 days.

- JNJ-56021927 (apalutamide) 240 mg (4×60-mg tablets); taken orally once daily with or without food

If a dose of apalutamide is missed on a given day, the missed dose should only be replaced in case that the patient remembers within a 12-hour window. Over the 12-hour window, the dose should be omitted and not be made up or taken with the next dose the following day. Please refer to the pharmacy manual/study-site investigational product manual for further details. Refer to the Site Investigational Product and Procedures Manual (SIPPM) for detailed guidance on study intervention dosage and administration. Apalutamide will be manufactured and provided under the responsibility of the sponsor. Refer to the IB for a list of excipients.²⁴

All participants will receive a stable regimen of goserelin 3.6 mg as a GnRH agonist. Dosing (dose and frequency of administration) of goserelin 3.6 mg will be same as ones prescribed for prostate cancer (goserelin 3.6 mg once per cycle). Goserelin 3.6 mg will be provided by the sponsor.

See the SoA (Section 1.3) for details on timing of drug administration during PK collection. Study intervention administration (both apalutamide and goserelin 3.6 mg) must be captured in the source documents and the electronic case report form (eCRF).

6.2. Preparation/Handling/Storage/Accountability

Preparation/Handling/Storage

All study interventions must be stored at controlled temperatures according to the requirements on the drug product label and protected from light prior to use.

Refer to the pharmacy manual/study SIPPM for additional guidance on study intervention preparation, handling, and storage.

Accountability

The investigator is responsible for ensuring that all study intervention received at the site is inventoried and accounted for throughout the study. The study intervention administered to the participant must be documented on the intervention accountability form. All study intervention will be stored and disposed of according to the sponsor's instructions. Study-site personnel must not combine contents of the study intervention containers.

Study intervention must be handled in strict accordance with the protocol and the container label, and must be stored at the study site in a limited-access area or in a locked cabinet under appropriate environmental conditions. Unused study intervention must be available for verification by the sponsor's study site monitor during on-site monitoring visits. The return to the sponsor of unused study intervention will be documented on the intervention return form. When the study site is an authorized destruction unit and study intervention supplies are destroyed on-site, this must also be documented on the intervention return form.

Potentially hazardous materials containing hazardous liquids, such as used ampules, needles, syringes and vials, should be disposed of immediately in a safe manner and therefore will not be retained for intervention accountability purposes.

Study intervention should be dispensed under the supervision of the investigator or a qualified member of the study-site personnel, or by a hospital/clinic pharmacist. Study intervention will be supplied only to participants participating in the study. Returned study intervention must not be dispensed again, even to the same participant. Study intervention may not be relabeled or reassigned for use by other participants. The investigator agrees neither to dispense the study intervention from, nor store it at, any site other than the study sites agreed upon with the sponsor. Further guidance and information for the final disposition of unused study interventions are provided in the Study Reference Manual.

6.3. Measures to Minimize Bias: Randomization and Blinding

Randomization will not be used in this study. All participants will receive the same study intervention.

As this is an open-label study, blinding procedures are not applicable.

6.4. Study Intervention Compliance

The study site must maintain accurate records demonstrating dates and amount of study intervention received, to whom dispensed (participant by participant accounting), and accounts of any study intervention accidentally or deliberately destroyed. This inventory must be available for inspection by designated sponsor or regulatory authority representatives at any time and at the end of the study, reconciliation must be made between the amount of study intervention supplied, dispensed, and subsequently destroyed or returned to sponsor or its representative. Study intervention administration and dose compliance will be assessed at each study cycle, starting with Cycle 2. A count of all study intervention provided by the sponsor will be conducted during the treatment phase of this study.

The investigator or designated study-site personnel will be responsible for providing additional instruction to any participant who is not compliant with taking the study intervention. In the absence of toxicity, if the dose compliance is not 100%, then investigators or designated study-site personnel should reinstruct participants regarding proper dose procedures and the participant may continue study intervention.

6.5. Concomitant Therapy

Prestudy and concomitant therapies must be recorded in the appropriate section of the eCRF throughout the study beginning with the signing of the ICF until 30 days after the last dose of study intervention.

All therapies (prescription or over-the-counter medications, including vaccines, vitamins, herbal supplements; non-pharmacologic therapies such as electrical stimulation, acupuncture, special diets, exercise regimens, or other specific categories of interest) different from the study intervention must be recorded in the eCRF. Recorded information will include a description of the type of therapy, duration of use, dose and dose regimen, route of administration, and indication.

6.5.1. Permitted Medications

Examples of permitted medications are listed below:

- Symptomatic treatment: Supportive care, such as antibiotics, analgesics, transfusions, and diet, and concomitant medications for the symptomatic treatment of related toxicities (Grades 1 to 4) may be administered according to the standard of care at the site, and the treating physician's discretion, as clinically indicated.
- Chronic supportive therapies: Ongoing supportive therapies are permitted.
- Palliative radiotherapy: Radiotherapy for symptomatic control is permitted, but should not include any radiation to target lesions.
- Surgical intervention may be permitted if disease could be resected radically due to the effect of the study intervention but must be approved by the sponsor's medical monitor on an individual basis prior to implementation.

6.5.2. Suggested Therapy

Fracture, fall, and hypothyroidism are known risks associated with apalutamide. Participants should be evaluated for fracture and fall risk. Monitor and manage participants at risk for fractures according to established treatment guidelines and consider use of bone targeted agents. Participants are strongly encouraged to obtain an adequate intake of dietary calcium (at least 1,000 mg per day, including supplements if necessary) and vitamin D (at least 800-1,000 international units [or according to the product label-prescribing information in the country of residence] per day for adults 50 years of age and older) and to engage in regular exercise to maintain muscle strength and bone density.

Thyroid replacement therapy, when clinically indicated, should be initiated or dose-adjusted.

6.5.3. Prohibited Therapy

Concurrent enrollment in another investigational drug or device study is prohibited during the Treatment Phase.

The following medications are prohibited while on study until the end-of-treatment (EOT) visit. For drugs known to lower the seizure threshold or cause seizures, the administration should be avoided for 30 days after last dose of study intervention. The sponsor must be notified in advance (or as soon as possible thereafter) of any instances in which prohibited therapies are administered.

- Chemotherapeutic, biologic, or other agents with antitumor effect against SGC
- Antiandrogens (eg, bicalutamide, flutamide, enzalutamide, abiraterone acetate plus prednisone)
- 5- α reductase inhibitors
- Estrogens
- Progestational agents (eg, cyproterone acetate)
- Androgens

- Spironolactone
- Drugs known to lower the seizure threshold or cause seizures (Section 10.8, Appendix 8)

6.5.4. Restricted Concomitant Therapy

Highlights of PK drug interaction with apalutamide and restricted concomitant medications are summarized below. Refer to the IB and associated addenda for complete details on the drug interaction potential of apalutamide, which include examples of medication that 1) may influence the effect of apalutamide, and 2) their effects may be influenced by apalutamide.²⁴ Also, refer to the prescribing information of GnRH agonist for any other potential drug interaction that may influence the effect.

- Medications that inhibit CYP2C8 or CYP3A4: Coadministration of a strong CYP2C8 or CYP3A4 inhibitor is predicted to increase the steady-state exposure of the active moieties (sum of unbound apalutamide plus the potency-adjusted unbound N-desmethyl apalutamide). No initial dose adjustment is necessary; however, consider reducing the apalutamide dose based on individual tolerability. Mild or moderate inhibitors of CYP2C8 or CYP3A4 are not expected to affect the exposure of apalutamide.
- Effect of apalutamide on drug metabolizing enzymes: Apalutamide is a strong inducer of CYP3A4 and CYP2C19, and a weak inducer of CYP2C9 in humans. Concomitant use of apalutamide with medications that are primarily metabolized by CYP3A4, CYP2C19, or CYP2C9 can result in lower exposure to these medications. Substitution for these medications is recommended when possible or evaluate for loss of efficacy if medication is continued. Concomitant administration of apalutamide with medications that are substrates of uridine 5'-diphospho-glucuronosyltransferase (UGT) can result in decreased exposure. Use caution if substrates of UGT must be coadministered with apalutamide and evaluate for loss of efficacy.
- Effect of apalutamide on drug transporters: Apalutamide was clinically shown to be a weak inducer of P-glycoprotein (P-gp), Breast Cancer Resistance Protein (BCRP), and Organic Anion Transporting Polypeptide (OATP) 1B1. Concomitant use of apalutamide with medications that are substrates of P-gp, BCRP, or OATP1B1 can result in lower exposure of these medications. Use caution if substrates of P-gp, BCRP, or OATP1B1 must be coadministered with apalutamide and evaluate for loss of efficacy if medication is continued.
- Corticosteroids (oral, intravenous [IV], or intramuscular [IM]): due to possible resistance mechanisms, which may be contributed by glucocorticoid receptor signaling, concurrent use of corticosteroids during the study is not recommended. Short term use (≤ 4 weeks) will be allowed if clinically indicated; however, its use must be tapered off as soon as possible. Contact the sponsor's medical monitor on an individual basis if the corticosteroid use will exceed 4 weeks.
- Because ADT may prolong the QT interval, the concomitant use of medicinal products known to prolong the QT interval or medicinal products able to induce torsade de pointes such as class IA (eg, quinidine, disopyramide) or class III (eg, amiodarone, sotalol, dofetilide, ibutilide) antiarrhythmic medicinal products, methadone, moxifloxacin, antipsychotics, etc should be carefully evaluated.

6.6. Dose Modification

Any dose/dosage adjustment should be overseen by medically-qualified study-site personnel (principal or subinvestigator unless an immediate safety risk appears to be present).

Table 1 summarizes apalutamide dose modifications for drug-related toxicities. Dose modifications for drug-related rash are summarized in **Table 2**. Once the dose is reduced for drug-related toxicities, a re-escalation of the dose should be discussed with the sponsor (prior to the re-escalation). Refer to the prescribing information of GnRH agonist used for management of drug-related toxicities by GnRH agonist and appropriate treatment including discontinuation of study intervention.

Table 1: Dose Modifications of Apalutamide (Except for Rash, if Rash Occurs, See **Table 2)**

Severity	Number of apalutamide tablets
Grade 1 or 2	No change or hold until return to baseline, resume at same dose
≥Grade 3	Hold until Grade 1 or baseline, resume at same dose
Recurrence ≥Grade 3	Hold until Grade 1 or baseline; 2 dose reductions are allowed for recurrent treatment-related toxicity (180 mg [3 tablets] and 120 mg [2 tablets]). The dose could be reduced to 120mg/day directly in the investigator's discretion. Discontinue if toxicity persists after 2 dose reductions (reduction to 120 mg).
First occurrence of seizure of any grade or Grade 4 neurotoxicity	Discontinue

Note: Adverse events are graded according to NCI-CTCAE version 5.0

If the skin rash has any component of desquamation, mucosal involvement, or pustules, dosing with apalutamide will be stopped, the participant will be referred to a dermatologist for evaluation, and a skin biopsy will be recommended (in addition to the interventions listed in **Table 2**) and the skin rash eCRF will be completed. If the skin rash is Grade 3 or higher, the participant will be asked to consent to documentation by a photograph and further evaluation by dermatology should also be considered and the skin rash eCRF will be completed. The skin rash eCRF will also be completed if the skin rash leads to permanent discontinuation of study intervention.

Table 2: Management of Drug-related Rash

Severity	Intervention
Grade 1	
 • Continue apalutamide at current dose • Initiate dermatological treatment^a 
 ○ Topical steroid cream AND ○ Oral antihistamines • Monitor for change in severity^a
Grade 2 (or symptomatic Grade 1)^b	
 • At investigator discretion, hold apalutamide for up to 28 days • Initiate dermatological treatment^a 
 ○ Topical steroid cream AND ○ Oral antihistamines • Monitor for change in severity^a 
 ○ If rash or related symptoms improve, reinitiate apalutamide when rash is Grade ≤1. Consider dose reduction at by 1 or 2 dose levels at investigator discretion
Grade ≥3^d	
 • Hold apalutamide for up to 28 days • Initiate dermatological treatment^a 
 ○ Topical steroid cream AND ○ Oral antihistamines AND ○ Consider short course of oral steroids • Reassess after 2 weeks (by site staff), and if the rash is the same or has worsened, initiate oral steroids (if not already done) and refer the participant to a dermatologist 
 ○ Reinitiate apalutamide at 1 or 2 dose level reduction^c when rash is Grade ≤1 at investigator discretion ○ If the dose reduction will lead to a dose less than 120 mg, the study intervention must be stopped (discontinued) • If after 28 days, rash has not resolved to Grade ≤1, contact the sponsor to discuss further management and possible discontinuation of study intervention

Note: Rash may be graded differently according to the type of rash and associated symptoms. For example, maculopapular rash is graded by body surface area covered and not severity of the rash. Please consult NCI-CTCAE version 5.0 for specific grading criteria for other types of rash.

^a Obtain bacterial/viral cultures if infection is suspected

^b Participant presents with other rash-related symptoms such as pruritus, stinging, or burning

^c If a participant previously started oral corticosteroids continue for at least 1 week after resumption of reduced dose of apalutamide. If the proposed total oral steroid use will exceed 28 days, contact the sponsor.

^d If there is blistering or mucosal involvement, stop apalutamide dosing immediately and contact the sponsor

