7. DISCONTINUATION OF STUDY INTERVENTION AND PARTICIPANT DISCONTINUATION/WITHDRAWAL

7.1. Discontinuation of Study Intervention

For all participants in the study, discontinuation from study intervention will not result in automatic withdrawal from the study. A participant's study intervention must be discontinued if:

- The participant withdraws consent to receive study intervention
- The investigator believes that for safety reasons or tolerability reasons (eg, AE) it is in the best interest of the participant to discontinue study intervention
- The participant becomes pregnant Refer to Section 10.5, Appendix 5, Contraceptive Guidance and Collection of Pregnancy Information
- Noncompliance with continued treatment or procedure requirements that the sponsor considers would impact the study evaluation despite frequent corrective instruction
- Documented radiographic (RECIST version 1.1) disease progression
- More than 2 dose level reductions for treatment-related AEs (Table 1 and Table 2)
- Seizure of any grade or Grade 4 neurotoxicity
- The participant receives concurrent (non-protocol) anticancer treatment

If a participant discontinues study intervention for any reason but does not withdraw consent for follow-up, then the scheduled assessments must be continued according to the follow-up phase in the SoA (Section 1.3). The EOT visit should be conducted within 30 days after the last dose of study intervention. The reason(s) a participant discontinues study intervention will be recorded on the eCRF. Once a participant discontinues treatment with the study intervention, the participant will not be permitted to be retreated.

In instances where the investigator feels a participant may continue to receive clinical benefit from further treatment with study intervention after documented disease progression, the case should be discussed with the sponsor's medical monitor, who in conjunction with the investigator, will determine if treatment beyond RECIST version 1.1 defined progression is indicated. If the participant is treated beyond documented disease progression, disease assessments will continue according to the schedule in Section 1.3 and the investigator and sponsor medical monitor will review clinical benefit after each disease assessment.

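### The any-grade rash stop in Protocol Section 6.6 omits blistering, and the only rule that names it is marked on the Grade 3 or higher row of Table 2

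*Protocol*

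**What the plan says.** Protocol Section 6.6 handles rash in two places.

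The running text gives a rule based on features: "If the skin rash has any component of desquamation, mucosal involvement, or pustules, dosing with apalutamide will be stopped". The participant is then referred to a dermatologist, a skin biopsy is recommended, and the skin rash form is completed. These steps apply "in addition to the interventions listed in" Table 2. The rule has no grade condition; the sentence after it opens a separate rule for Grade 3 or higher.

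Table 2 gives actions by grade:

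- Grade 1: "Continue apalutamide at current dose", with topical steroid and antihistamine.
- Grade 2 or symptomatic Grade 1: "At investigator discretion, hold apalutamide for up to 28 days". Footnote b explains the symptomatic part: "Participant presents with other rash-related symptoms such as pruritus, stinging, or burning".
- Grade 3 or higher: a hold of up to 28 days, then restart at a reduced dose or discontinuation. This row carries marker d, whose footnote reads "If there is blistering or mucosal involvement, stop apalutamide dosing immediately and contact the sponsor".

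A note under the table covers grading: "Please consult NCI-CTCAE version 5.0 for specific grading criteria for other types of rash".

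Table 1 excludes rash by its title. Section 7.1 requires discontinuation when "The investigator believes that for safety reasons or tolerability reasons (eg, AE) it is in the best interest of the participant" to stop. It names neither rash nor blistering.

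**The concern.** The two stop rules have different trigger lists. Mucosal involvement is on both. Blistering is only on the list attached to Grade 3 or higher, although footnote d shows that the sponsor regards it as needing an immediate stop.

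A site that follows the Grade 1 or Grade 2 row literally could therefore keep dosing a participant who has that same feature. The participant would also miss the dermatology referral and biopsy recommendation in the running text. Protocol Section 2.2 reports a mean elimination half-life of about 7 days after a single dose in healthy men, so a late stop cannot be undone quickly.

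What is at stake is the consistency of a safety instruction across sites. The primary analysis is not involved.

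**Working it through.** The plan gives no figure to reproduce. The check compares the rules and traces one case through them.

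**Step 1: the two stop rules side by side.**

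| | Section 6.6 running text | Table 2 footnote d |
|---|---|---|
| Desquamation | listed | not listed |
| Pustules | listed | not listed |
| Mucosal involvement | listed | listed |
| Blistering | not listed | listed |
| Grade condition in the words | none | none |
| Where it is attached | any drug-related rash | marker on the Grade 3 or higher row only |
| Action | stop, dermatology referral, biopsy recommended, rash form | stop at once, contact the sponsor |

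**Step 2: trace a rash with blistering and none of the other three features.**

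- Grade 3 or higher: footnote d applies, so a stop is mandatory.
- Grade 2 or symptomatic Grade 1: the running text is not triggered. The row carries marker b, not d. The hold is optional.
- Grade 1 without symptoms: the running text is not triggered and the row carries no marker d. The instruction is to continue.

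**Step 3: look for another rule.** Table 1 does not apply to rash. Section 7.1 requires discontinuation only once the investigator has formed a judgement about safety. A Grade 1 rash can reach the optional Grade 2 hold through footnote b, whose symptom list is open, but that is again a judgement. The SAP lists skin rash as an event of special interest (Section 6.2) and sets no dosing rule. Nothing else in either document gives a dosing instruction for blistering.

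**Step 4: can the case arise?** It needs an isolated blistering rash to be gradable as 1 or 2. The protocol says that maculopapular rash is graded by the area covered and not by severity, but it gives this for that rash type only and sends other types to CTCAE v5.0. That source is not available here, so the answer is a range. If blistering is always Grade 3 or higher, the gap is empty. If it can be Grade 1 or 2, the gap is open on both lower rows.

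**Step 5: context for frequency.** Protocol Section 2.2 reports skin rash in 24.3% and 27.1% of apalutamide-treated men in the two Phase 3 prostate cancer studies, mostly Grade 1 or 2. If those rates carried over to 24 participants, 24 × 0.243 = 5.8 and 24 × 0.271 = 6.5, so about 6 would have a rash of any kind. The share with isolated blistering is not given, so the number affected by the gap cannot be derived.

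**The case against.** The best reply is that footnote d already covers the case. Its words contain no grade limit, and only the position of one superscript restricts it. A careful site might apply it to any rash. Superscripts are also easily misplaced when a table is read from a PDF, so the printed Table 2 should be looked at. This part stands: some sites may already act correctly. It does not remove the point, because a footnote ordinarily applies where it is marked, and a mandatory safety stop should not depend on how a site reads a marker.

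Second, the gap may be empty, either because CTCAE v5.0 grades such a rash as 3 or higher, or because a site counts blistering as a component of desquamation, a term the protocol does not define. This also stands, and the conclusion is conditional for that reason.

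Third, investigators are not forced to keep dosing. Medically qualified staff oversee dose changes, the Grade 2 row allows a hold, and Section 7.1 requires discontinuation once the investigator judges that safety calls for it. A reader might infer that the protocol obliges sites to dose through a worrying blistering rash; the documents do not support that. The backstops are nevertheless discretionary, while the other three features have a stop that is not.

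A reader might also infer that the Grade 1 instruction to continue contradicts the any-grade stop for desquamation, pustules or mucosal involvement. That does not hold. The running text is specific and mandatory, Table 2 is the general grade ladder, and the ordinary reading is that the specific rule decides dosing while the table's other measures are added.

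**Conclusion.** The point holds in a conditional form. The any-grade stop leaves out blistering, and the only rule that names it is marked for Grade 3 or higher. If an isolated blistering rash can be graded below 3, Table 2 as written directs continued dosing at Grade 1 and an optional hold at Grade 2 or symptomatic Grade 1, with only judgement-based safeguards behind it.

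This rests on three assumptions: CTCAE v5.0 permits such a grade, blistering is not read as desquamation, and marker d is on the printed page only where it appears to be. The first two cannot be settled from the documents.

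The importance is minor. It is a wording mismatch in a safety rule, with partial safeguards and no estimable number of participants. Counting how many feature-and-grade combinations lack a stop would only tally the wording and say nothing about risk. A reader might also suspect an effect on the response rate result. The documents give no ground for that: the response definition, the boundaries and the analysis populations do not depend on this rule.

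**What to change.** Add blistering to the list of features in the Section 6.6 running text. That one word brings an isolated blistering rash of any grade under the mandatory stop, the dermatology referral, the biopsy recommendation and the skin rash form.

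Marking footnote d on all three rows of Table 2 is an optional alignment. It would make the table agree with the text for blistering and mucosal involvement, but would also require sponsor contact for those two features at lower grades. There is no need to extend footnote d to desquamation or pustules: they already have an any-grade stop, and nothing in the documents calls for immediate sponsor contact when they occur.

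The cost is a protocol wording amendment, which under Section 10.3 needs ethics committee or review board approval before it is implemented, plus notice to sites. Sample size, error rates, endpoints and analyses stay as they are. If blistering turns out always to be Grade 3 or higher, the added word does no harm.
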